## **1. Introduction**

### **1.1 Study Abstract:**

Acetylsalicylic acid, or aspirin, is a cyclooxygenase inhibitor with antiplatelet and anti-inflammatory properties. Aspirin has been shown in multiple studies to be an effective medication to prevent or delay the onset of preeclampsia in pregnancy. While most guidelines recommend low-dose aspirin for this indication, there is no consensus on the optimal dose. Practitioners have used and described doses in the literature ranging from 50mg to 162mg daily.

This document describes a protocol of a randomized trial of women evaluating whether using 162mg of aspirin daily more adequately inhibits thromboxane-mediated platelet function, compared to a dose of 81mg daily. Within the population taking 162mg of aspirin daily, we will compare platelet function when taking a once-daily dose of 162mg of aspirin, compared to taking 81mg twice daily.

### **1.2 Study Hypothesis:**

In women, taking 162mg of aspirin daily has improved inhibition of platelet function, compared to a dose of 81mg daily.

### **1.3 Purpose of the Study Protocol**

This protocol describes the background, design and organization of the randomized clinical trial. Institutional Review Board (IRB) approval will be obtained prior to beginning recruitment.

## **2. Background**

### **2.1 Introduction**

Preeclampsia is a multi-system disorder affecting up to 10% of all pregnancies, and is part of the spectrum of hypertensive disorders of pregnancy. There is well established evidence that low-dose aspirin is an effective medication for use to prevent or delay the onset of preeclampsia in patients at increased risk. Low-dose aspirin is very safe to use in pregnancy, with no significant maternal or fetal risks. This safety profile has been demonstrated in multiple large studies.

However, there remains much controversy and lack of evidence surrounding the optimal dosing of aspirin for this indication. Interestingly, studies have suggested a dose-response relationship between aspirin and preeclampsia reduction effect.

### **2.2 Biological Mechanisms**

The etiology and pathogenesis of preeclampsia are multifactorial, and are characterized by an abnormal vascular response to placentation, resulting in increased vascular resistance, enhanced platelet aggregation, activation of the coagulation system, and endothelial cell dysfunction. This is thought to be at least partially the result of an increased thromboxane A2 levels, and reduced prostacyclin levels. These effects can be demonstrated as early as 13 weeks in at-risk pregnancies. Low-dose aspirin has been shown to counteract this imbalance; aspirin inhibits cyclooxygenase-1 and its thromboxane production. This explains aspirin's effectiveness as a preventative medication for preeclampsia. Treatment with 81mg of aspirin, starting between 12 and 16 weeks of gestation, is associated with an at least 8% reduction in the onset of preeclampsia during that pregnancy.

However, there is evidence to suggest that failure of low-dose aspirin in preventing preeclampsia may be related to incomplete inhibition of platelet aggregation at the recommended dosage, or "aspirin resistance". In fact, by increasing using a dose of 162mg instead of 81mg, the rate of aspirin resistance drops from approximately 30% to around 5%.

There is data to suggests that dosing aspirin at bedtime results in somewhat better morning platelet inhibition. Also, twice-daily aspirin dosing, compared to once-daily dosing, has been persistently shown in the literature to be associated with improved platelet inhibition.

## 2.3 Aspirin and Obesity

Obesity is known to be a risk factor for developing preeclampsia in pregnancy. While the pathophysiology of this risk is not completely understood, the etiology is likely multifactorial.

The pathophysiologic changes resulting from obesity may alter the pharmacokinetics of medication in this population, including aspirin. This may result in an increased likelihood of aspirin resistance in this population, resulting in incomplete inhibition of cyclooxygenase-2, and therefore persistent normal or elevated serum thromboxane levels.

In addition, obesity in and of itself has been associated with platelet hyperreactivity, which is evident both with and without aspirin use. This may in part be due to enhanced lipid peroxidation leading to low-grade inflammation, which in turn results in an increase in thromboxane-dependent platelet activation.

Interestingly, mature human adipose tissue has also been found to express and release soluble fms-like tyrosine kinase 1 (sFlt-1), and both BMI and body weight have been shown to affect the rate of expression of this molecule in adipose tissue. sFlt-1 is an anti-angiogenic molecule which has been correlated with and predictive of the onset of preeclampsia. Aspirin has been shown to inhibit the production of sFlt-1 in cytotrophoblasts when induced by hypoxia, and if these findings prove to be generalizable, this may suggest that different aspirin dosages are needed to inhibit a larger amount of circulating sFlt-1.

Finally, thromboxane B2 is a validated serum marker for measuring platelet response to aspirin therapy. The levels of thromboxane B2 in obese women have been shown to be significantly

elevated when compared to a non-obese cohort, suggesting possible underlying increased platelet aggregation in the obese patient.

## **2.4 Aspirin-Triggered 15-Epi-Lipoxins**

One of the more recent proposed mechanisms of action for use of ASA is its ability to initiate biosynthesis of novel anti-inflammatory mediators by means of interactions between endothelial cells and leukocytes. These mediators are classified as aspirin-triggered 15-epi-lipoxins (ATLs). Such compounds may account at least in part for some aspirin's clinical benefits, which are distinct from the well-appreciated action of aspirin as a platelet inhibitor. Thus, the protective actions of ATL are likely to underlie some of the therapeutic impact of aspirin when aberrant inflammation is a component of disease pathogenesis, such as in PE.

## **2.5 Exosome and aspirin dosing**

To date, professional societies recommend use of low-dose aspirin for preeclampsia prevention in pregnant individuals at high-risk of developing the disease, but the optimal dose is unknown. Furthermore, there are limited biomarkers available as candidates for monitoring therapeutic response to aspirin treatment in pregnant individuals at high-risk for PE, which ultimately may be used to generate desirable data to optimize aspirin dosing and improve pregnancy outcomes. Recent advancement in isolating specific extracellular vesicles (exosomes; 40–160 nm) from maternal blood and characterizing their cargo content have helped to better understand the response to therapeutic interventions. Although diagnostic potential of exosomes has been reported, no studies have examined the response to therapeutic interventions such as different doses of aspirin on exosomes.

## **2.6 Rationale for Randomized Trial and Hypothesis**

Due to the known pharmacokinetic effects of aspirin, and the known increased incidence of aspirin resistance in this population, we hypothesize that the use of 162 mg daily will have lower incidence of aspirin resistance, when compared to a once-daily 81mg of aspirin.

### **3. Study Design**

#### **3.1 Primary Research Question**

This randomized trial will address the primary research question:

In women, does taking 162mg of aspirin daily, starting between 12 and 16 weeks of gestation, result in a lower incidence of aspirin resistance, when compared to a daily dose of 81mg?

#### **3.2 Secondary Research Questions**

Secondary research questions that this study will address are whether in pregnant women, a daily aspirin dose of 162mg, compared to a daily dose of 81mg, starting between 12 and 16 weeks of gestation, will decrease the risk of:

- Preeclampsia;
- Gestational hypertension;
- Gestational diabetes;
- Composite maternal cardiovascular outcome;
- Composite maternal morbidity, including postpartum hemorrhage;
- Operative vaginal delivery, cesarean delivery;
- Neonatal morbidity and mortality.

#### **3.3 Design Summary**

This study is a non-blinded prospective randomized trial of pregnant women with a singleton pregnancy between 12 weeks 0 days and 16 weeks 0 days gestation. Participants will be randomized to receive either:

- Aspirin 81mg daily at bedtime until delivery;
- Aspirin 162mg daily at bedtime (2x 81mg tablets) until delivery;

#### **3.4 Eligibility Criteria**

### **3.4.1 Inclusion Criteria**

- Females older than 18 years of age;
- The patient is physically and mentally able to understand the informed consent and is willing to participate in this study;
- The patient is between 12 weeks 0 days and 16 weeks 0 days of gestation at the time of enrollment. Gestational age will be determined by last menstrual period, confirmed with a first trimester ultrasound, per the recommended guidelines by the American College of Obstetricians and Gynecologists.
- One high risk factor or at least 2 moderate risk factors for preeclampsia

### **3.4.2 Exclusion Criteria**

- Known allergy or reaction to aspirin, or concurrent medical condition where the use of aspirin is contraindicated;
- Use of aspirin prior to enrollment in the study;
- Known or suspected fetal anomaly or aneuploidy;
- Prisoners;
- Prenatal care or planned delivery outside the Ohio State University.

### **3.5 Informed Consent Criteria**

Women will be approached at the time of one of their prenatal visits prior to 16 weeks to determine study eligibility. Voluntary oral permission will be obtained to participate in the screening process. Respondents who do not wish to participate in the screening process will be thanked and no further questions asked.

Written informed consent will be obtained before enrollment into the study. A copy of the consent form will be provided to the patient. Women who are not fluent in English will be enrolled by a person fluent in their language, if possible. Both verbal and written informed consent and authorization will be obtained in that language; if this is not possible the patient will be excluded.

### **3.6 Randomization Method**

Patients will be randomized to either 81mg of daily aspirin or 162mg of daily aspirin at bedtime, starting between 12 weeks 0 days and 16 weeks 0 days of gestation.

## **4. Study Procedures**

### **4.1 Screening for Eligibility and Consent**

Women will be approached at the time of one of their prenatal visits prior to 16 weeks to determine study eligibility. If the patient elects to participate in the study and signs the relevant consents, the patient's chart will be reviewed to ensure that the patient meets inclusion and exclusion criteria.

If a patient agrees to participate, and meets the inclusion and exclusion criteria, she will be asked to sign the consent form for participating in the study.

### **4.2 Randomization**

Patients will be randomized to taking either 81mg daily or 162mg daily of aspirin. If the patient is below 12 weeks of gestation, she will be asked to start taking the medication at 12 weeks 0 days at bedtime. If the patient is between 12 weeks 0 days and 16 weeks 0 days gestation, she will be asked to start taking the medication at bedtime on the day of enrollment. The aspirin pills will be provided to the patient on the day of randomization.

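### Do the below-12-weeks branch in Section 4.2 and the singleton limit missing from Section 3.4 let ineligible women into the trial?

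*Combined protocol and SAP*

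**What the plan says.** **Gestational age.** The inclusion list in Section 3.4.1 states: "The patient is between 12 weeks 0 days and 16 weeks 0 days of gestation at the time of enrollment". Section 3.3 describes the population as "pregnant women with a singleton pregnancy between 12 weeks 0 days and 16 weeks 0 days gestation". Section 4.2 has two branches. For the earlier woman: "If the patient is below 12 weeks of gestation, she will be asked to start taking the medication at 12 weeks 0 days". For the woman already in the window: "she will be asked to start taking the medication at bedtime on the day of enrollment". It then adds: "The aspirin pills will be provided to the patient on the day of randomization".

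**Approach and check.** Sections 3.5 and 4.1 give an upper limit for approach and no lower one: "Women will be approached at the time of one of their prenatal visits prior to 16 weeks to determine study eligibility". Section 3.5 places consent first: "Written informed consent will be obtained before enrollment into the study". Section 4.1 says that the "chart will be reviewed to ensure that the patient meets inclusion and exclusion criteria".

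**Number of fetuses.** The singleton limit stands in Section 3.3 only. The four inclusion items in Section 3.4.1 and the five exclusion items in Section 3.4.2 do not mention it. The risk-factor item names no factors, so it does not supply the limit either.

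**The concern.** On gestational age, a woman below 12 weeks does not meet Section 3.4.1, yet Section 4.2 tells her when to start her tablets and does so under the randomization heading. Read literally, that suggests she could be allocated before she is eligible. The trial is not blinded, so an interval would then open between a known allocation and the first dose. A woman who left in that interval would be allocated but never treated.

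On singletons, Section 4.1 has staff check charts against the inclusion and exclusion criteria. If those lists are all that staff consult, a twin pregnancy passes. That would bear on secondary outcomes such as preterm birth, cesarean delivery, birth weight and NICU admission. Section 4.7.3 has no rule for counting two infants of one mother.

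**Working it through.** The point depends on no sample-size, power or event figure, so there is no number in the plan to reproduce. The check is a count and a comparison of the sections.

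**Counts**

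- Listed criteria: 4 inclusion + 5 exclusion = 9. Those that mention the number of fetuses: 0.
- Sections that state the singleton limit: 1 (Section 3.3).
- Approach statements: 2 (Sections 3.5 and 4.1). Those with a lower gestational limit: 0.
- Sections that give the aspirin start window: 4 (Sections 3.1, 3.2, 3.6 and 4.2). All four agree on 12 to 16 weeks.

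**Three ways to read the below-12-weeks branch**

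| Reading | What happens | Fits Section 3.4.1? |
|---|---|---|
| A. The full check is made when she is approached early | She fails on gestational age, and the branch applies to nobody | Yes |
| B. She is approached or consented early and enrolled once she reaches 12w0d | The branch tells her in advance when she will start | Yes |
| C. She is randomized below 12 weeks | She is allocated before meeting the criterion | No |

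Reading C requires the gestational-age item to be skipped in a check that Section 4.1 places before Section 4.2. The text does not direct this. Section 4.2 refers to the day of enrollment only for women already in the window. For the earlier woman it fixes only the first dose. An approach window open below 12 weeks is what one would expect under reading B.

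**What reading C would do if it happened**

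1. Aspirin would still start at 12w0d, inside the window.
2. The thromboxane sample at randomization (Section 4.7.1) would still precede study aspirin, and Section 3.4.2 excludes women who used aspirin before enrollment. It would remain a pre-treatment value, taken somewhat earlier.
3. Some women might be allocated and never treated. That can happen to any woman handed tablets in an open-label trial. The documents give no number for it.

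**Singletons**

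1. Section 3.3 is part of the same Study Design chapter as the lists in Section 3.4, and it states the limit outright. Nothing in Section 3.4 contradicts it; the lists are silent.
2. If a multiple pregnancy did slip in, allocation is 1:1 (Section 5.2), so such pregnancies would be expected to balance between arms on average. The result would be some noise and a slightly different population for the obstetric and neonatal secondary outcomes. It would not be a systematic difference between doses.
3. The primary outcome is measured in the mother, so counting infants does not arise there.

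**The case for a change.** The strongest case for acting is that staff work from the eligibility lists and not from a design summary, and that no reading of Section 3.4 supplies the singleton limit. On gestational age, no section says how consent, eligibility check, enrollment and randomization are ordered. Section 4.1 itself is unclear: one paragraph puts the chart review after consents are signed, and the next puts signing the study consent form after the criteria are met. Two coordinators could therefore record the same woman differently, one as eligible and one as a deviation.

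Much of this stands as a comment on drafting. The singleton omission is real and is the firmer of the two points. The order of steps is undefined, and the passages would read better if reconciled. What does not stand is the step from there to harm. The gestational-age point is ambiguous timing, not an instruction to allocate ineligible women. The singleton point assumes that staff disregard a restriction the protocol states. Section 5 does not define an analysis population, but that gap exists whether or not this branch is in the protocol and should not be charged to it.

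**Conclusion.** The observations are correct and the concern does not hold as a statistical defect. Read as a whole, the protocol limits the trial to singletons, checks eligibility before randomization and starts aspirin between 12 and 16 weeks in every section that gives the window. Its effect on the primary outcome and on power is nil as far as the documents show. The number of women affected cannot be derived from them. The sponsor can tidy the wording whenever the protocol is next amended, but no design feature or analysis depends on it.

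This rests on two assumptions: that staff treat Section 3.3 as binding alongside the lists in Section 3.4, and that the check in Section 4.1 covers gestational age before allocation. If the first failed, the damage would be limited to noise in some secondary outcomes. If the second failed, some women would be allocated early and a few might never be treated. Whether the sample size in Section 5.2 is adequate is a separate question that this point does not touch.

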#### 4.3 Baseline Procedures

The patient's eligibility information will be collected, including gestational age and estimated date of delivery, in addition to the following:

- Demographics: age, race, insurance status;
- Medical history: pre-pregnancy weight, current weight, height, current blood pressure, past medical history;
- Social history: marital status, years of education, alcohol use, tobacco use and other maternal drug use;
- Obstetrical history: previous miscarriages and terminations, history of preeclampsia or other obstetric complications in prior pregnancies.

All patients have a baseline prenatal panel test via a lab draw and a urine specimen as part of their routine prenatal care. We will ask the patient to allow us to obtain additional blood tubes during the same draw, therefore not exposing the patient to added needle sticks. This will test for aspirin-triggered 15-epi-lipoxins, exosomes, placental growth factor levels, soluble fms-like tyrosine kinase 1 levels, thromboxane levels, serum creatinine, and liver function tests.

Patients also provide a urine sample at each prenatal visit. The patient will be asked to allow us to collect part of the urine sample to evaluate for baseline proteinuria by dipstick, and to measure urine thromboxane levels and the urine protein to creatinine ratio.

The patient will be asked to allow us to collect 10 inches of umbilical cord just after their delivery to measure prostaglandins and 15-epi-lipoxins.

#### 4.4 Patient Management and Follow Up

Patients will continue to receive standard prenatal care with their treating physician. Patients typically have their blood pressure and weight measured at all prenatal visits, and this information will be collected.

Patients typically have a second trimester lab draw at approximately 27 weeks of gestation. We will ask the patient to allow us to obtain additional blood tubes during the same draw, therefore not exposing the patient to added needle sticks. This will test for aspirin-triggered 15-epi-lipoxins, exosomes, thromboxane levels, placental growth factor levels and soluble fms-like tyrosine kinase 1 levels. A urine sample will also be collected on that visit, to measure urine thromboxane levels.

Study personnel will meet with participants monthly, at the time of prenatal care visits, to ascertain compliance with study agent, query for side effects or complications, and to chart abstract medical/obstetrical complications and recorded blood pressure.

All other obstetric care is at the discretion of the primary provider, including but not limited to: treatment of maternal medical comorbidities or obstetric complications, timing and frequency of antenatal ultrasound, maternal and fetal surveillance, and timing and mode of delivery.

#### **4.5 Procedures on Labor and Delivery and Postpartum**

At delivery, study personnel will chart abstract maternal and infant delivery information and maternal and infant data will be collected until day of discharge or up to 30 days postpartum, whichever occurs first.

Patients typically have a blood draw in the third trimester. We will ask the patient to allow us to obtain additional blood tubes during the same draw, therefore not exposing the patient to added needle sticks if possible. These will test for aspirin-triggered 15-epi-lipoxins, exosomes, thromboxane levels, placental growth factor levels, and soluble fms-like tyrosine kinase 1 levels. A urine sample will also be collected to test for urine thromboxane levels.

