#### **4.6 Adverse Event Reporting**

Detailed information concerning adverse events will be collected and evaluated throughout the conduct of the protocol. Adverse events will be reported to the Institutional Review Board per policy.

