### **4.7.2 Maternal Secondary Outcomes**

- Diagnosis of eclampsia, HELLP, atypical HELLP, preeclampsia, superimposed preeclampsia or antepartum gestational hypertension, using standard American College of Obstetricians and Gynecologists criteria, during the pregnancy or up to 30 days postpartum;
- Placental growth factor levels and soluble fms-like tyrosine kinase 1 levels, to evaluate whether the values are predictive of aspirin resistance, as the ratio of both values has been validated as a predictor of preeclampsia;
- Aspirin-triggered 15-epi-lipoxins;
- Gestational diabetes by oral GTT criteria performed after randomization;
- Preterm birth < 34 weeks and < 37 weeks, both spontaneous and indicated;
- Operative vaginal delivery and cesarean delivery;
- Estimated and quantitative blood loss;
- Blood transfusion;
- Epidural hematoma;
- Maternal morbidity and adverse maternal outcomes, including venous thromboembolism, peripartum cardiomyopathy, massive transfusion and postpartum hemorrhage, ICU admission, and maternal death.

The maternal plasma exosome proteome profile

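### Data collection ends at discharge, but the preeclampsia-spectrum outcome is defined to 30 days postpartum, so later diagnoses are not captured under the stated procedures

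*Combined protocol and SAP*

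**What the plan says.** Section 4.5 sets the method and the stopping point for delivery and postpartum data. The method is chart review: "study personnel will chart abstract maternal and infant delivery information". The stopping point is given in the same sentence: "maternal and infant data will be collected until day of discharge or up to 30 days postpartum, whichever occurs first". Day 30 is thus only a cap for long stays; for anyone discharged earlier, collection ends at discharge.

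Section 4.7.2 defines the first maternal secondary outcome as any of a group of hypertensive diagnoses made "during the pregnancy or up to 30 days postpartum". Within that group, the list ends with "superimposed preeclampsia or antepartum gestational hypertension". Gestational hypertension is therefore limited to the antepartum period. Preeclampsia, superimposed preeclampsia, eclampsia, and HELLP (typical or atypical) are not.

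Section 3.2 puts preeclampsia first among the secondary questions. It gives no postpartum window of its own; the 30 days come from 4.7.2.

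**The concern.** The outcome definition and the collection rule have different end points. Limiting one component to the antepartum period and leaving the others open to day 30 shows that postpartum diagnoses were meant to count. Section 4.5, followed as written, cannot supply those that are first made after the woman has gone home.

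The plan does not say how such a case would be coded. If a woman with no recorded diagnosis at discharge is counted as event-free, the reported 30-day rate is too low in both arms. A reader would take it as a 30-day rate when it is a rate through discharge, with a cut-off that varies from woman to woman with length of stay.

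**Working it through.** **1. The two windows side by side.**

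- Collection ends at min(d, 30), where d is the postpartum day of discharge (4.5).
- The outcome window ends at day 30 (4.7.2).
- Gap = max(0, 30 − d) days. It is zero only if discharge is on or after day 30.

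The documents give no discharge day. With assumed values:

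- d = 1: 29/30 = 97% of the postpartum window uncollected
- d = 3: 27/30 = 90%
- d = 7: 23/30 = 77%

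These are shares of days, not of diagnoses.

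**2. Does another section fill the gap?**

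- Section 4.4: "Study personnel will meet with participants monthly, at the time of prenatal care visits". Those contacts end with the pregnancy.
- Section 4.6: "Detailed information concerning adverse events will be collected and evaluated throughout the conduct of the protocol". It states no postpartum window, contact or method, and no link to outcome ascertainment.
- Section 6 covers the database, access rights and sample transfer only.
- No postpartum visit, call or post-discharge chart review is described.

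**3. Which outcomes are affected.** The gap concerns the five diagnoses that may be made postpartum. Gestational hypertension is unaffected. The morbidity item ("including venous thromboembolism, peripartum cardiomyopathy, massive transfusion and postpartum hemorrhage, ICU admission, and maternal death") has no stated window, so it does not contradict 4.5 and is not part of this point. The primary outcome (4.7.1) is last sampled at admission for delivery, before the gap begins.

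**4. Effect on the comparison.** The plan states no event rate, effect measure or power for this outcome, so there is no figure to reproduce. What follows is sensitivity only. Let p be the full-window rate (assumed 5 to 20%) and s the share of events first diagnosed after discharge (assumed 5 to 20%), equal in both arms. Take the arm risks as about equal for the standard errors, and let q = p(1 − s).

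- Risk ratio: p₂(1 − s) / [p₁(1 − s)] = p₂/p₁, unchanged.
- SE of log risk ratio: multiplied by √{[(1 − q)/q] / [(1 − p)/p]}.
- Risk difference (RD): multiplied by (1 − s).
- SE of RD: multiplied by √{q(1 − q) / [p(1 − p)]}.

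The sample size cancels from all of these ratios. Worked case, p = 0.10 and s = 0.20, so q = 0.08: SE(log RR) × √(11.5/9) = 1.130; SE(RD) × √(0.0736/0.09) = 0.904; RD/SE × 0.80/0.904 = 0.885.

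| p | s | SE(log RR) | RD | SE(RD) | RD/SE |
|---|---|---|---|---|---|
| 0.05 | 0.05 | ×1.027 | ×0.95 | ×0.976 | ×0.973 |
| 0.05 | 0.20 | ×1.124 | ×0.80 | ×0.899 | ×0.890 |
| 0.10 | 0.05 | ×1.029 | ×0.95 | ×0.977 | ×0.972 |
| 0.10 | 0.20 | ×1.130 | ×0.80 | ×0.904 | ×0.885 |
| 0.20 | 0.05 | ×1.032 | ×0.95 | ×0.981 | ×0.969 |
| 0.20 | 0.20 | ×1.146 | ×0.80 | ×0.917 | ×0.873 |

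The SE of the risk difference does not widen. It falls by less than the difference itself, so the signal relative to noise drops.

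**5. In events and power (control risk and risk ratio assumed).** With 128 women per arm (the figure in 5.2), an assumed control risk of 20% and an assumed risk ratio of 0.65, expected events are 128 × (0.20 + 0.13) = 42.2. At s = 0.20 they are 128 × (0.16 + 0.104) = 33.8. Two-sided 5% power goes from 32.5% to 26.2%.

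**The case against.** The best case against has four parts.

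- **Incidental capture.** Adverse-event collection in 4.6 has no discharge cut-off, and 3.4.2 keeps prenatal care and planned delivery at one institution. Some readmissions could therefore come to light. This stands as a limit on the wording: the diagnoses are not captured under the stated procedures, which is not proof that every one would be lost. But chance discovery is not ascertainment, and the plan does not say such cases would enter the outcome.
- **Size.** Discharge day, lost share and event rate are all assumed, and a share of days says little about a share of diagnoses. This also stands. What the documents alone support is 30 − d uncovered days and an unknown number of missed cases.
- **Importance.** Aspirin is planned only until delivery (3.3), so the uncovered days all follow treatment. The outcome is secondary and the sample size was not built on it. Equal proportional loss leaves the risk ratio alone, and nothing in the documents shows unequal loss. This limits the weight of the point. It does not remove the mismatch, since the plan itself chose to count diagnoses to day 30.
- **Reading.** Thirty days might be meant as an outer limit in both sections, with 4.5 as the operational stop. Section 4.7.2 does not say so, and on that reading its outcome would still need rewording.

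**Conclusion.** The concern holds. Sections 4.5 and 4.7.2 cannot both be followed: for every woman discharged before day 30, part of the defined outcome window is never collected, and nothing else in the plan supplies it. The result would be an undercount of unknown size in the preeclampsia-spectrum rate.

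Under the assumed ranges (p and s each 5 to 20%, loss equal in both arms), the risk ratio is essentially unchanged with its log-scale SE up 3 to 15%. The risk difference falls by 5 to 20%, its SE by 2 to 10%, and their ratio by 3 to 13%. Unequal loss would also bias the risk ratio, but the documents give no sign of it. The primary outcome and the sample size are not touched. The point should be corrected; it does not threaten the trial's main result.

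**What to change.** Amend 4.5 so that preeclampsia, superimposed preeclampsia, eclampsia and HELLP (typical or atypical) are abstracted from the chart through 30 days postpartum for every woman, regardless of discharge date. In the same edit, say whether diagnoses made at other institutions will be sought, and whether the mother's or the infant's discharge ends the remaining collection.

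The cost is one or two sentences and one later chart review per woman, up to the 400 in 5.2, using the abstraction method the study already has. No visit or procedure is added. The change would go to the IRB as an amendment, with a check that the consent and authorization cover the later review. One limit remains: 3.4.2 ties only prenatal care and planned delivery to the institution, so postpartum diagnoses made elsewhere may still be missed.

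As a fallback, restate the 4.7.2 window as ending at discharge from the delivery admission. That needs no extra collection and makes definition and data agree, but it gives up the post-discharge diagnoses that the plan set out to count.
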